10.3 Inferential Analyses

No formal hypothesis testing is planned

10.4 Ocular PK analysis

An undiluted vitreous sample will be collected at the time of vitrectomy to assess ONL1204 drug levels. A separate summary and listing will be provided for the same. Considering the sampling limitations, no ocular PK analysis will be applicable for this study and hence concentration listings and summaries along with figures will be provided based on ocular PK population.

11. PHARMACODYNAMICS

Pharmacodynamic statistical analyses will be conducted based on the proteomic analysis of cytokine biomarkers in ocular fluids.

The following PD endpoints will be assessed:

- Vitreous Humor sample collected at pre-injection baseline by vitreous tap
- Vitreous Humor sample from the undiluted sample collected at the time of surgery
- Aqueous Humor sample collected at the time of surgery

Analyte concentrations will be provided for the vitreous humor and aqueous humor samples.

All PD endpoints will be analyzed separately by ONL Therapeutics.

12. EFFICACY

No formal efficacy analyses are planned for this study, however exploratory endpoints will be evaluated.

13. SAFETY

Safety endpoints (adverse events, clinical laboratory evaluations, vital signs, BCVA, ophthalmic imaging, intraocular pressure, and other safety assessments) will be analyzed using the safety population. Safety endpoints (continuous and categorical) will be summarized descriptively as described in section 3.1.

13.1.1 Adverse Events

All AEs will be coded using MedDRA. All AE summaries will be restricted to TEAEs only. Summary tables will include the number of participants (%) experiencing an event and the number of events. Participants will be counted only once for each SOC and PT level (categorical descriptive analysis).

Ocular and non-ocular AEs will be reported separately. Ocular AEs will be split into study eye/fellow eye/Both eye events.

The TEAE summaries will include:

- Overall summary of TEAEs.
- TEAE summary by SOC and PT.
- TEAE summary of serious adverse events (SAE) by SOC and PT.
- TEAE summary by SOC, PT and Severity.
- TEAE summary by SOC, PT, and relationship to study drug.
- TEAE summary by SOC, PT, and relationship to procedure.
- TEAE summary of events leading to the study drug removal by SOC and PT.

All listings will be presented by the safety population. Separate listings will be provided for patients with SAEs, AEs leading to withdrawal from the study and AEs resulting in death, if any.

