4.2 Dose Limiting Criteria and Maximum Tolerated Dose

4.2.1 Dose Limiting Criteria

Dose limiting toxicity, if observed, will be declared by the SRC, based on their review of the relevant clinical information.

Determination of dose limiting toxicity will include consideration of the following events:

- 1. Ocular inflammation increases by 2 units from pre-injection on the Standardization of Uveitis Nomenclature (SUN) grading scale for aqueous cell or vitreous haze, secondary to inflammation and not the drug formulation itself, identified post-injection of ONL1204 and prior to retinal reattachment surgery;
- 2. Sustained elevation of IOP characterized as > 30 mmHg for 3 consecutive days, postinjection of ONL1204 and prior to retinal reattachment surgery, despite pharmacologic therapy;
- 3. Reduction in visual acuity from baseline after injection of ONL1204 and prior to retinal reattachment surgery, that in the opinion of the investigator is likely due to the investigational product and results in a:
 - a) Decrease in visual acuity from 20/200 or 20/400 to light perception without progression of the underlying retinal detachment; or
 - b) Decrease in visual acuity from baseline to no light perception.
- 4. Any serious adverse event (SAE) that occurs within the first 14 days following ONL1204 injection that, in the opinion of the investigator, is related to ONL1204.

Page 23 of 52

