9.3.1.1 Adverse Events

Adverse events will be coded to a Medical Dictionary for Regulatory Activities (MedDRA) preferred term and system organ classification. The occurrence of treatmentemergent AEs will be summarized using MedDRA preferred terms, system organ classifications, and severity. TEAEs are defined as adverse events that occurred or worsened following the first administration of study medication. Separate summaries of treatment-emergent SAEs and TEAEs considered related to study treatment and AEs leading to study treatment discontinuation will be generated. All AEs will be listed for individual patients showing both verbatim and preferred terms.

Ocular and systemic AEs will be reported separately. Ocular AEs will be split into study eye and fellow eye events. Events reported in 'both' eyes will be counted in the study and fellow analysis. Separate causality analyses will be performed for the study eye events (related to drug and related to procedure); for fellow eye and systemic events, causality will be assessed based on study drug alone.

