- Actual Time from First Dose (hours) = (Date/Time of First Dose PK Sample collection) (Date/Time of First Dose)
- Actual Time Deviation (hours) = (Actual PK Sample Collection Time Post Dose) (Scheduled PK Sample Collection Time Post Dose).
- Treatment Emergent Adverse Events (TEAEs) are defined as adverse events that occurred following the first administration of study medication.

Inferential Analyses

Descriptive statistics will be used to summarize the safety, PD and PK data. No formal hypothesis testing is planned.

Multiple Comparisons and Multiplicity Adjustments.

Not applicable for this study.

Handling of Missing Data

For the classification of Treatment emergent adverse event (TEAE) and Concomitant medication, the following will be applied in the following order:

- a. If all dates/times (start and stop) missing, the event/medication will automatically be classified as a TEAE/Concomitant medication.
- b. For AEs with a missing start date/time, if the event end date/time is prior to first study drug administration, the event will not be classified as a TEAE.
- c. If only the AE start year/ medication end year is present and is the same or is after the first study drug administration year unit, the event/medication will be classified as a TEAE/Concomitant medication.
- d. If the AE start month and year/medication end month and year are present and are the same or after the first study drug administration month and year units, the event/medication will classified as a TEAE/Concomitant medication.

For plasma concentration-time data/profiles and PK analysis the following will be applied:

- a. Concentrations that are below limit of quantification (BLQ) prior to the dosing (Pre-dose) will be set equal to zero. Post dose BLQ concentrations will be set to zero.
- b. Where there are no results, these will be set to missing.
- c. If more than 75% of values per nominal timepoint and treatment group are BLQ, then all descriptive statistics, except for nBLQ, will be denoted as not calculable (NC).
- d. For the purpose of calculating the non-compartmental plasma PK parameters, concentrations that are BLQ prior to the first quantifiable value will be set equal to zero and BLQ values after measurable concentrations will be set to zero.
- e. For the calculation of summary statistics of plasma PK parameters, all NR (not reported) and NC (not calculable) values in a data series will be set to missing.

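### No planned adverse event table is split at vitrectomy, so a post-operative event can absorb a pre-operative event of the same term in the patient count and the severity row

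*SAP*

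**What the plan says.** **Start of the period.** SAP section 3 (Key Definitions) takes treatment-emergent events to be "adverse events that occurred following the first administration of study medication". Protocol 9.3.1.1 is slightly wider: "adverse events that occurred or worsened following the first administration of study medication". Neither definition has a boundary at surgery. Under Protocol 8.6, events are monitored to the exit visit or 30 days after study drug, whichever is longer; here that is the Week 24 exit.

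**Counting.** SAP 13.1.1 says: "Summary tables will include the number of participants (%) experiencing an event and the number of events". It then adds: "Participants will be counted only once for each SOC and PT level". The severity tables in SAP section 18 (14.3.3.4 and 14.3.3.4a) are by maximum severity, with no period stated.

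**Attribution.** SAP 13.1.1 plans a "TEAE summary by SOC, PT, and relationship to study drug" and a "TEAE summary by SOC, PT, and relationship to procedure". Neither is by period.

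**Surgery.** Protocol 4.1 and the SAP's design description place vitrectomy 3 or more days after injection and give no maximum. Protocol 1.2.1 expects it within 7 days of injection.

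**The protocol's own window.** Dose-limiting criterion 1 in Protocol 4.2.1 covers inflammation found "post-injection of ONL1204 and prior to retinal reattachment surgery". Criteria 2 (pressure) and 3 (visual acuity) have the same limits. Criterion 4 (related serious events) runs for 14 days after injection instead.

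**The concern.** Adverse event reporting is the first primary endpoint, and all patients receive study drug, so there is no control arm to show what vitrectomy alone would produce. Several of the product risks in Protocol 1.4.1, such as intraocular inflammation, raised pressure and visual loss, are also plausible after intraocular surgery. Timing of onset relative to surgery is therefore informative, and the protocol uses it for three of its four dose-limiting criteria.

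The tables discard that timing. A reader of the study report would see, per cohort and term, one patient count and one maximum severity covering a few days before surgery and about five months after it. Two cohorts with different pre-operative experience can give the same patient row and the same severity row.

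**Working it through.** The documents state no event rates, power or calculated sample size, so there is no planned figure to reproduce. The check has three parts.

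**1. What the counting rules do.** Take one patient with a mild event before surgery and a moderate event of the same term after it, recorded separately.
- Patient count for the term: 1, the same as with the post-operative event alone.
- Severity row: moderate, the same as with the post-operative event alone.
- Event count: 2 instead of 1, but nothing shows that one of them was pre-operative.

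**2. Length of the window.** Inputs: follow-up 24 weeks × 7 = 168 days (Protocol 4.1); surgery from 3 days (Protocol 4.1) to 7 days (Protocol 1.2.1) after injection. Share = days to surgery / 168.

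| Surgery, days after injection | Share before surgery | Days after surgery | Ratio after : before |
|---|---|---|---|
| 3 | 3/168 = 1.8% | 165 | 55 |
| 7 | 7/168 = 4.2% | 161 | 23 |
| 14 (assumed; no maximum is stated) | 14/168 = 8.3% | 154 | 11 |

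This is a share of time, not of events. Risk will not be uniform over 168 days, so the table does not measure how many events are absorbed.

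**3. Illustration for a cohort of 4.** Let a be the risk of a term before surgery and b the risk of the same term after it, taken as independent. Both are assumptions. Pooled risk = 1 − (1 − a)(1 − b).
- a = 0, b = 50%: pooled risk 50%, so 4 × 0.50 = 2.0 patients expected.
- a = 25%, b = 50%: pooled risk 1 − 0.75 × 0.50 = 62.5%, so 4 × 0.625 = 2.5 patients expected.
- A pre-surgery column would expect 0 and 4 × 0.25 = 1.0 patients respectively.
- Chance of 3 or more of 4 in the pooled row: 31% with a = 0, 52% with a = 25%.
- Chance of at least 1 of 4 in the pre-surgery column: 0% with a = 0, and 1 − 0.75⁴ = 68% with a = 25%.

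With a = 25%, the expected excess in the pooled row is 0.75, 0.50 or 0.25 of a patient for b = 25%, 50% or 75%; in the pre-surgery column it is 1.0 throughout. Under independence, the share of pre-operative cases that add nothing to the patient count equals b by construction, so it is not an estimate of absorption in this trial.

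**The case against.** A reader might infer that drug events before surgery are hidden. The documents do not support that:
- Event counts are planned beside patient counts, so a separately recorded recurrence still shows as an extra event.
- A pre-operative event judged drug-related appears in the drug-relationship table, and Protocol 9.3.1.1 calls for separate drug and procedure causality analyses for the study eye.
- All adverse events are listed by patient. With 4 patients per cohort, onset can be read against surgery by hand, and SAP 13.1.8 lists the retinal examination separately before and after surgery.
- Anterior chamber cell, vitreous haze, pressure and visual acuity are summarised by visit. Visit 2 precedes surgery, and Table 4-1 requires all Visit 3 procedures to precede it.

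A reader might also infer that the maximum tolerated dose is at risk. It is not on this account. Under Protocol 4.2 and 10.2 the safety review committee decides from clinical data cohort by cohort, while these tables follow database lock.

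Nor is pre-surgery onset the only objective evidence or a clean measure of drug effect. By-visit measurements are objective too. The window also contains the vitreous tap and the injection. Drug effects may appear after surgery, since Protocol 1.2.1 describes slow elimination from retina and iris-ciliary body, and Protocol 1.4.1 lists a less favourable surgical outcome as a product risk.

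All of this stands, but these safeguards have gaps:
- Event counts are not by period.
- Attribution is open-label, and *procedure* is undefined. Protocol 6.4.2 lists taps and injection as study procedures and vitrectomy as an additional one, while Protocol 1.4.4 says retinal surgery is not a study-specific risk.
- Table 4-1 requires daily visits while pressure exceeds 30 mmHg and allows other extra visits between Visits 2 and 3, but SAP section 3 keeps unscheduled values out of summary tables. ETDRS acuity is not scheduled at Visit 3.

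**Conclusion.** The point holds as a weakness in how a primary endpoint is tabulated. No planned adverse event table uses the boundary that the protocol applies in dose-limiting criteria 1 to 3. The once-per-term and maximum-severity rules let a post-operative event absorb a pre-operative one in two of the main summary rows. Splitting at surgery would separate drug, tap and injection effects together from vitrectomy effects; it would not separate drug from tap or injection.

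The window is about 1.8% to 4.2% of 168 days if surgery falls 3 to 7 days after injection, and longer if surgery is later. How often absorption would occur cannot be estimated from the documents, and the cohort illustration rests on assumed rates. The consequence is a less informative study report, not lost data or a compromised escalation decision. It is a cheap improvement.

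**What to change.** In SAP 13.1.1 and the section 18 table list:
- Split the study-eye parts of Tables 14.3.3.2, 14.3.3.4, 14.3.3.5 and 14.3.3.6 by onset: from injection to before vitrectomy, and on or after vitrectomy. Keep the overall column.
- Count each patient once per term, and take maximum severity, within each period.
- Assign the period from adverse event onset date and surgery date, with times where recorded. State a rule for onset on the day of surgery, because the documents do not show that surgery time is collected. State rules too for partial onset dates and for events that begin before surgery and worsen after it.
- Define *procedure* as tap/injection or vitrectomy, so that the relationship tables can be read.

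The split should need little or no new data: SAP section 3 already uses adverse event start dates and times and allows relative days from another reference date, and Visit 3 is the day of surgery. If the case report form has only one undifferentiated procedure-relationship field, the last item can only be a stated definition. The cost is a few extra columns with sparse cells at 4 patients per cohort.

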13.1.2 Safety Laboratory Assessments

Blood and urine samples will be collected at the time points specified in the Schedule of Events (refer to the Protocol) to conduct CBC, renal function, and hepatic function analyses.

The following tests will be performed within each of the specified test panels:

Complete blood count (including):

- While Blood Cell (WBC) count with differential
- Hemoglobin (hgb)
- Hematocrit (hct)
- Platelet count

Renal function test (including):

- Albumin
- Blood Urea Nitrogen (BUN)
- Bicarbonate
- Calcium
- Chloride
- Creatinine
- eGFR

- Glucose
- Phosphorus
- Potassium
- Sodium

Hepatic Function tests (including):

- Alanine transaminase (ALT)
- Alkaline phosphatase (ALP)
- Albumin
- Total protein
- Aspartate transaminase (AST)
- Bilirubin
- Prothrombin time (PT)

All laboratory data collected at scheduled and unscheduled visits will be included in the listings, but only results collected at scheduled visits will be included in the summary tables.

Results for individual parameters may be reported in different units depending on the analyzing laboratory. If required, the results (and the corresponding normal range cut-off values) for individual parameters may be converted to International System of Units (S.I.) to summarize the data.

For all the parameters where a unit value has been reported, the parameter names that will be used in the outputs will comprise of the test name and the unit of measure, for example, 'Albumin (g/L)'. For the urinalysis parameters, the parameter name will be the reported test name only. Parameters will be sorted alphabetically within tables and listings.

For all parameters where a normal range limit value was reported, the normal range will be derived based on the available lower and upper limit values and any reported mathematical symbols. If both a lower and upper limit value is available, the normal range will be presented as '(Lower, Upper)'.

The reported results for each parameter with a defined normal range will be classified ('Low', 'Normal', 'High') in relation to the defined normal range limits. If a result is equal to the normal range cut-off value, the result will be considered 'Normal'.

The complete blood count, renal function test and hepatic function test result tables will present summary statistics for each laboratory parameter. For each parameter, summaries will be presented for the baseline and each scheduled post-baseline visit. In addition, summaries will be presented for the change from baseline values at each scheduled post-baseline visit (continuous descriptive analysis).

The decimal precision to which the summary for each parameter is reported will be based on the maximum number of decimals to which the reported result or the normal range limits are presented to in the raw data. The results and normal ranges will be displayed to the same decimal precision in the listings.

13.1.3 Vital Signs

The following vital signs measurements will be taken at the time points specified in the Schedule of Events (refer to the Protocol):

- Heart Rate (beats/min)
- Sitting Systolic Blood Pressure (SBP) (mmHg)
- Sitting Diastolic Blood Pressure (DBP) (mmHg)
- Respiratory Rate (breaths/min)

• Temperature (°C)

All vital signs data collected at scheduled and unscheduled visits will be included in the listings, but only results collected at scheduled visits will be included in the summary tables.

The parameter names that will be used in the outputs will comprise of the test name and the unit of measure, for example, 'Systolic Blood Pressure (mmHg)'. Parameters will be sorted in the order that the measurements were collected in on the Vital Signs eCRF page within the tables and listings.

Vital signs measurements will present summary statistics for the results at the baseline and each scheduled post-baseline visit for each of the parameters. In addition, summaries will be presented for the change from baseline values at each scheduled post-baseline visit (continuous descriptive analysis).

The decimal precision to which the summary for each parameter is reported will be based on the maximum number of decimals to which the results were reported on the eCRF.

13.1.4 Ophthalmologic Assessments

The following parameters will be assessed in study eye and contralateral eye for Safety Population.

13.1.5 Best Corrected Visual Acuity (BCVA)

BCVA will be performed in the study eye and fellow eye using the logMAR score. The logMAR score will be converted from the ETDRS visual acuity measure at time points specified in the Schedule of Assessments (refer to protocol) to assess visual acuity.

LogMAR (Logarithm of the minimal angle of resolution) score will be calculated using the formulae logMAR = -0.02 * ETDRS + 1.7

If the patient cannot read the ETDRS chart at 1 meter, the assessment result reported in counts fingers, hand motions, light perception, or no light perception will be utilized and converted to a logMAR score ($CF = 2.0 \log MAR$, $HM = 3.0 \log MAR$, $LP = 3.9 \log MAR$, $NLP = 4.0 \log MAR$). BCVA will be performed prior to procedures requiring pupil dilation.

LogMAR BCVA will be assessed and summarized as described in section 3.1 (continuous descriptive analysis) in study eye and fellow eye:

Summary of total letters read for each eye along with change from baseline will be presented by visit for both eyes (continuous descriptive analysis). All other assessments will be listed.

Low Luminance ETDRS BCVA and Low Contrast ETDRS BCVA will also be summarized as continuous variables only.

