16 patients will be enrolled and treated, starting with the lowest dose, Cohort 1. The first patient in each cohort will be observed for at least 14 days post surgery (through Visit 5) before the rest of the cohort can be enrolled. The safety review committee will review the data prior to clearing the sentinel patient and enrolling the remainder of the cohort. After all 4 patients in a cohort have completed Visit 5, the safety review committee will review available safety data to determine if dose limiting toxicity exists that prohibits enrolling the next higher dose cohort. The respective IRB's will be informed of the outcome of the SRC meetings.

If there are no safety concerns, the next cohort will start treatment.

*Patients may be replaced who do not receive an injection of study medication, or for discontinuing from the study for reasons unrelated to treatment before completing Visit 4.

Page 8 of 52

TABLE OF CONTENTS

CLINICAL RESEARCH PROTOCOL						
Clinical Protocol Approval Form2						
Confidentiality and Investigator Statement						
Study Summary	4					
TABLE OF CONTENTS	8					
Table of Tables	.10					
Table of Figures	.10					
LIST OF ABBREVIATIONS	.11					
1 INTRODUCTION AND RATIONALE	.14					
1.1 Background	.14					
1.2 ONL1204	.14					
1.2.1 Preclinical Experience	.14					
1.2.2 Clinical Experience	.16					
1.3 Study Rationale	.16					
1.3.1 Rationale for the Proposed Doses	.16					
1.3.2 Rationale for Pharmacokinetic testing	.17					
1.3.3 Rationale for Vitreous Tap and Pharmacodynamic Analysis	.17					
1.4 Potential Risks and Benefits	.18					
1.4.1 Potential Risks of Study Product	.18					
1.4.2 Potential Risk to Fetal Development	.18					

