3 STUDY ENDPOINTS

3.1 Primary Endpoints

The primary endpoints will be the safety profile demonstrated in this study, including:

- Adverse event reporting
- Clinical evaluations including BCVA
- Clinical laboratory evaluation

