3. STATISTICAL CONSIDERATIONS

Data will be handled and processed per the sponsor's representative (Novotech) Standard Operating Procedures (SOPs), which are written based on the principles of good clinical practice (GCP).

General Considerations

All data collected on the electronic case report form (eCRF) will be presented in the data listings and will be listed and sorted by cohort, participant number and visit, where applicable. All descriptive summaries will be presented by cohort and nominal visit/time point (where applicable).

All safety, PD and PK descriptive summaries will be presented by cohort. All disposition and, concomitant medication descriptive summaries will be presented by cohort and nominal visit/time point (where applicable).

Unless otherwise stated, the following methods will be applied:

• Continuous variables: Descriptive statistics will include the number of non-missing values (n), arithmetic mean, standard deviation (SD), median, minimum, and maximum values.

The minimum and maximum values will be displayed to the same decimal precision as the source data, the arithmetic mean, SD, and median values will be displayed to one more decimal than the source data for the specific variable.

95% Confidence Intervals (CIs), mean differences (among treatments and from baseline) and least-square (LS-Means) values will be displayed to one more decimal than the source data for a specific variable. P-values will be displayed to 3 decimal places.

The appropriate precision for derived variables will be determined based on the precision of the data on which the derivations are based, and statistics will be presented in accordance with the above-mentioned rules.

• PK data: The actual blood sampling dates and times relative to dosing time will be listed by participant and nominal sampling time, with time deviation calculated, for all participants with available plasma and vitreous concentration data, including participants excluded from the PK population. Individual (for each participant) and mean concentrations over time will be displayed graphically in linear and semi-logarithmic plots of concentrations versus time. The actual collection time will be used for individual plasma concentration curves and the nominal time will be used for the plots of mean plasma concentration curves. Similar plot will be provided using vitreous concentration.

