18. TABLES

Table Number	Table Title	Population
14.1	Demographics and Other Baseline Characteristics	
14.1.1	Summary of Subject Enrolment and Disposition	ITT
14.1.2	Demographics and Baseline Characteristics	ITT
14.2	PK/PD	
14.2.1	Plasma ONL1204 Concentrations (unit) by Treatment and Time	РК
14.2.2	Plasma ONL1204 Pharmacokinetic Parameters by Treatment	РК
		РК
14.3	Safety	
14.3.1	Concomitant Medication by ATC Classification	Safety
14.3.3	Adverse Events	
14.3.3.1	Summary of Overall Treatment Emergent Adverse Events	Safety
14.3.3.2	Incidence of Ocular Treatment-Emergent Adverse Events by SOC and PT	Safety
14.3.3.2a	Incidence of Non-Ocular Treatment-Emergent Adverse Events by SOC and PT	Safety
14.3.3.3	Incidence of Serious Ocular Treatment-Emergent Adverse Events by SOC and PT	Safety
14.3.3.3a	Incidence of Serious Non- Ocular Treatment-Emergent Adverse Events by SOC and PT	Safety
14.3.3.4	Incidence of Ocular Treatment-Emergent Adverse Events by SOC, PT and Maximum Severity	Safety
14.3.3.4a	Incidence of Non-Ocular Treatment-Emergent Adverse Events by SOC, PT and Maximum Severity	Safety
14.3.3.5	Incidence of Ocular Treatment-Emergent Adverse Events by SOC and PT and relationship to study drug	Safety
14.3.3.5a	Incidence of Non-Ocular Treatment-Emergent Adverse Events by SOC and PT and relationship to study drug	Safety
14.3.3.6	Incidence of Ocular Treatment-Emergent Adverse Events by SOC and PT and relationship to procedure	Safety
14.3.3.6a	Incidence of Non-Ocular Treatment-Emergent Adverse Events by SOC and PT and relationship to procedure	Safety
14.3.4	Laboratory Parameters	
14.3.4.1	Hematology Results - Change of Hematology Values	Safety
14.3.4.2	Hematology Results – Normal/Abnormal Shift Table	Safety
14.3.4.3	Chemistry Results - Change of Chemistry Values	Safety
14.3.4.4	Chemistry Results – Normal/Abnormal Shift Table	Safety
14.3.5	Other Safety	
14.3.5.1	Vital Signs - Values and Change from Baseline	Safety
14.3.6.1	Summary of Best Corrected Visual Acuity (BCVA) (Letters)	Safety

Novotech – Strictly Confidential

2022-09-14

Table Number	Table Title	Population
14.3.6.2 14.3.6.3 14.3.6.4 14.3.6.5 14.3.6.6	Summary of Best Corrected Visual Acuity (BCVA) (LogMAR Values) Summary of Low Luminance and Low Contrast BCVA Indirect Ophthalmoscopy Summary of Biomicroscopy Examination Summary of Intraocular Pressure (mmHg)	Safety Safety Safety Safety Safety Safety
14.3.6.7 14.3.6.8	Summary of Pin Hole Visual Acuity Summary of Log Contrast Sensitivity Scores	Safety Safety

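### BCVA is tabulated only as a continuous variable, so no BCVA table counts the eyes that lost vision or shows from what level

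*SAP*

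**What the plan says.** Protocol 3.1 lists "Clinical evaluations including BCVA" among the primary endpoints. Protocol 4.2.1 item 3 describes dose-limiting visual harm eye by eye and by category: from 20/200 or 20/400 to light perception (LP), or "Decrease in visual acuity from baseline to no light perception" (NLP). Both apply after injection and before reattachment surgery.

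For the analysis, SAP 13.1.5 says "Summary of total letters read for each eye along with change from baseline will be presented by visit for both eyes (continuous descriptive analysis"). SAP section 3 defines that kind of summary: "Descriptive statistics will include the number of non-missing values (n), arithmetic mean, standard deviation (SD), median, minimum, and maximum values". Section 18 lists two standard BCVA tables: 14.3.6.1 in letters and 14.3.6.2, "Summary of Best Corrected Visual Acuity (BCVA) (LogMAR Values"). No table of loss categories, no acuity shift table and no table of the 4.2.1 visual criteria is planned. The phrase "will also be summarized as continuous variables only" in the same section refers to low-luminance and low-contrast BCVA. For standard BCVA, the continuous-only plan follows from the text and the table list.

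SAP 13.1.5 converts letters to logMAR and codes off-chart vision as counts fingers (CF) 2.0, hand motion (HM) 3.0, LP 3.9 and NLP 4.0. It gives no letter value for those eyes. SAP section 3 keeps unscheduled values out of summary tables.

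**The concern.** Cohorts have four patients ("After all 4 patients in a cohort have completed Visit 5", Protocol, Study Schematic). Baseline is a detached macula with acuity between 20/100 and HM (Protocol 5.2), and every study eye then has repair surgery (Protocol 4.1). Change from baseline at the post-surgical visits therefore mixes surgical recovery with any harm, and a mean or median averages one eye's loss against the other eyes' recovery.

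The safety question is how many eyes lost vision at each dose, and from what level. The planned BCVA tables do not state that. The SAP does use categories elsewhere: hematology and chemistry have normal/abnormal shift tables (14.3.4.2, 14.3.4.4), and slit-lamp and ophthalmoscopy gradings are summarised categorically. The one clinical evaluation that the primary endpoint names has neither.

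**Working it through.** The documents state no figure to reproduce here. The check applies the SAP's own coding to hypothetical cohorts of 4. The individual acuities are assumptions.

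**Inputs.** logMAR = 1.7 - 0.02 x letters (SAP 13.1.5), so 50 letters = 0.7 (20/100) and 70 letters = 0.3 (20/40). Off-chart codes are as above. Positive logMAR change is loss. Scheduled ETDRS BCVA is at Visits 1 and 2 (before surgery) and Visits 6, 7 and 8 (Weeks 6, 9 and 24, after surgery), from Protocol Table 4-1.

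**1. When the averages hide a loss L in one of four eyes.**
- Mean: (L - sum of the other three gains)/4 < 0 when those three gain more than L/3 on average. For L = 0.6 (30 letters) this is 0.20. For HM to NLP (L = 1.0) it is 0.33; for CF to NLP (L = 2.0), 0.67; for 20/100 to NLP (L = 3.3), 1.10.
- Median: if three eyes improve, the second and third ordered changes are both improvements, whatever the size of L.

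**2. Examples, logMAR change.**

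| Cohort | Changes | Mean | Median | Max |
|---|---|---|---|---|
| Three HM to 20/40; one 20/100 to NLP | -2.7, -2.7, -2.7, +3.3 | -1.20 | -2.7 | +3.3 |
| HM, CF, 35 letters to 60, 65, 70 letters; one 20/100 to NLP | -2.5, -1.6, -0.7, +3.3 | -0.375 | -1.15 | +3.3 |
| Three 20/100 to 75 letters; one 20/100 to NLP | -0.5, -0.5, -0.5, +3.3 | +0.45 | -0.5 | +3.3 |
| Three HM to 20/40; one HM to NLP | -2.7, -2.7, -2.7, +1.0 | -1.775 | -2.7 | +1.0 |
| Two HM to 20/40; two HM to NLP | -2.7, -2.7, +1.0, +1.0 | -0.85 | -0.85 | +1.0 |

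The third row shows that hiding in the mean is conditional. The last two rows have the same maximum change (+1.0) and the same maximum value (4.0), with one and two eyes lost.

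**3. The maximum does not rank harm as Protocol 4.2.1 does.** HM to NLP is 4.0 - 3.0 = +1.0. 20/100 to CF is 2.0 - 0.7 = +1.3. The first is an acuity change listed in item 3; the second is not, yet it gives the larger maximum.

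**4. Letters table.** The SAP gives no rule for off-chart eyes, so take both possibilities.
- Scored 0: four HM eyes, three reaching 60 letters and one reaching NLP, give changes 60, 60, 60, 0 (mean +45, median +60, minimum 0). HM and NLP are indistinguishable. At Visit 2, an HM eye falling to NLP with the others unchanged gives 0 for every letters change.
- Left missing: change is then missing too (SAP Key Definitions). In the third row above, the letters table would show n = 3 and mean +25.

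**5. Pre-surgical window.** Visit 2 is the only scheduled post-injection BCVA before surgery. Additional visits before surgery are at the investigator's discretion, so BCVA taken at one is unscheduled and reaches listings but no BCVA table.

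**The case against.** The other side has a good deal.

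- Minimum and maximum are planned ("arithmetic mean, standard deviation (SD), median, minimum, and maximum values"), so an NLP eye seen at a scheduled visit appears as logMAR maximum 4.0. A reader might infer that a blind eye would be invisible; the documents do not support that.
- With four complete logMAR changes, all four can be recovered: minimum and maximum are two of them, twice the median is the sum of the middle two, and the SD fixes their difference, up to rounding. The information is present, but it has to be solved for. That needs all four eyes, and it needs logMAR change to be tabulated. SAP 13.1.5 names change only for letters; logMAR change rests on the general rule in Key Definitions and on Protocol 9.3.1.4.
- A reader might also infer that nothing in the report counts visual loss. Protocol 7.11 makes a clinically relevant fall in acuity an adverse event, and SAP 13.1.1 counts participants with ocular events, split by eye. Listings 16.2.11.1 and 16.2.11.2 give individual values. Adverse event counts depend, however, on investigator judgement, and 7.11 asks for signs of a common pathology to be merged into one event. They are not counts of eyes crossing an acuity threshold.
- Visit 2 is before surgery, so repair cannot mask a loss there.

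These points narrow the concern. They do not supply a BCVA table that says how many eyes lost vision, or from what level.

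**Conclusion.** The gap is real and of moderate weight. At Weeks 6, 9 and 24 the mean and median of a 4-eye cohort can both improve while one eye loses vision. For the median it is enough that three eyes improve; for the mean their average gain must exceed L/3, which is 0.33 to 1.10 logMAR for a fall to NLP from the eligible baseline range. No BCVA table gives the number of eyes with loss or their starting level, the letters table has no rule for off-chart eyes, and unscheduled values are left out.

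A reader might infer that the maximum tolerated dose would be set on masked averages. The documents do not support that. The Safety Review Committee declares dose-limiting toxicity from clinical review (Protocol 4.2.1, 10.2), deciding on each cohort after Visit 5, before any post-surgical ETDRS BCVA is scheduled. The visual criteria apply before surgery, and the SAP tables follow database lock (SAP section 16). What is affected is the reported safety profile by dose.

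The examples rest on assumed acuities. The L/3 condition and the median result do not.

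**What to change.** Keep Tables 14.3.6.1 and 14.3.6.2. Add to SAP 13.1.5 and section 18:

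1. **Counts of eyes with loss.** n/N by cohort, eye and scheduled visit, with Day 2 shown separately as pre-surgical, plus an any-post-injection-visit row that includes unscheduled values. Count loss from baseline of at least 0.30 logMAR (15 letters) and at least 0.60 logMAR (30 letters), or any step down through CF, HM, LP and NLP, so that the count does not hang on the spacing of the codes. Add n/N study eyes showing the acuity changes already listed in Protocol 4.2.1 item 3.
2. **Shift table.** Acuity category at baseline against each visit and against the worst value, with on-chart categories fine enough to show loss in fellow eyes, which enter at 20/60 or better.
3. **Two sentences of definition.** State that logMAR change from baseline is tabulated, and how off-chart eyes enter the letters table.

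The 0.30 and 0.60 cut-offs are reporting conventions, not taken from the documents. The cost is SAP wording and one or two tables from data already collected, with no new visits or patients. If the SAP can no longer be changed, section 4 allows the tables to be reported as post hoc.

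The limit is precision. Counts in cohorts of 4 make events visible but do not estimate rates: 1/4 has an exact 95% interval of 0.6% to 80.6%, and 0/4 still has an upper limit of 60.2%.
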